9. EFFICACY ANALYSES

Due to the method of action of the INT230-6 therapy observed over the course of the study, proper assessment utilizing RECIST or iRECIST was not possible. A response across all lesions using sum of diameters to assess efficacy over time using response criteria was not utilized. Thus, efficacy analyses will largely focus on the response of individual tumors (injected and bystander) as opposed to an overall tumor response, and any overall response will utilize the modified response criteria defined below.

Efficacy analyses will be conducted on the All Treated Population (ATP), the Response Evaluable Population (REP), and the Scan Evaluable Population (SEP). RECIST 1.1 assessments were not collected. Rather injected tumor response and non-injected tumor response utilizing some of the RECIST criteria were evaluated. Sponsor utilized RECIST principles with the injected and non-injected tumor measurements obtained. Efficacy will be determined based on a modified version of RECIST 1.1 criteria. Specifically, complete response (CR) and partial response (PR) will be defined for injected tumors followed per RECIST 1.1 utilizing target lesions. Progressive disease will be determined by clinical or radiological deterioration leading to the subject being taken off-treatment at the discretion of the investigator. Stable disease (SD) is defined as any adequate assessment not considered CR, PR, or progression. The appearance of a new lesion will not necessarily be considered progression and if possible will be assessed. Any post-baseline visit where a target lesion present at baseline was not assessed will result in a Not Evaluable (NE) assessment for that lesion. Data will be presented by treatment and, when indicated, by subgroups.

The primary efficacy parameter is the disease control rate (DCR), defined as the number of subjects obtaining a best overall response of either CR, PR, or SD as described above divided by the total number of subjects in the analysis population. The DCR will be presented with accompanying 95% exact binomial confidence intervals for each study part for the ATP population, REP, SEP, and by subgroup.

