9.2. Progression-Free Survival and Overall Survival

Progression free survival (PFS) and Overall Survival (OS) will be evaluated for the All Treated Population, the REP, and the SEP. PFS will be defined as the time (in months) from first dose of INT230-6 to either observation of clinical deterioration, removal from study, or occurrence of death due to any cause within 126 days (approximately 2 time intervals for tumor assessments) of the last tumor assessment. Progression date will be defined as the end of treatment date as captured per eCRF guidelines when the reason for end of treatment is either 'Radiographic

deterioration' or 'Clinical deterioration.' In subjects without a progression date or with a death date more than 126 days after the last tumor assessment, the PFS time will be censored on the date of last tumor assessment or last treatment date if the subject has no post-baseline tumor assessments. PFS analyses will consider tumor assessments after treatment discontinuation.

OS will be defined as the time (in months) from first dose of INT230-6 to death. Subjects for whom death is not reported will be censored at the date of end of study.

PFS and OS will be summarized in a listing. The median time to OS as obtained from Kaplan-Meier methods will be tabulated by subgroup and will include the median, 25th percentile, 75th percentile, and a 2-sided point-wise 95% confidence interval. Hazard ratios may be determined between certain curves for the Kaplan Meier figures noted below.

A Kaplan Meier figure of OS for the All Treated, REP, and SEP populations will be presented for each of the following:

- a curve all treated monotherapy patients, a curve for subjects that received a dose to total tumor burden < 40% of tumor burden, a curve for those subjects that had a dose to total tumor burden \geq 40%,
- a curve for escalation cohort combining A1, B1, EA, EC, and a curve for escalation cohort combining EC2 and EC3,
- a curve for sarcoma patients in the monotherapy cohort and a curve for monotherapy sarcoma patients having \geq 40% of their total tumor burden treated,
- a curve for the pembrolizumab DEC/DEC2 combined cohort for subjects,
- a curve for all ipilimumab FEC cohort subjects,
- a curve for the ipilimumab FEC sarcoma subjects, a curve for all monotherapy sarcoma patients and a curve for monotherapy sarcoma subjects having \geq 40% of their total tumor burden treated will be included.

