APPENDIX 1.

The following information provides additional programming instructions to define important variables that are not available in the main SAP text.

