5. PROGRESSION DEFINITION

Progression is defined as a patient who radiographically or clinically deteriorated as captured on any number of forms designating the patient is ending treatment or death. This includes the end of treatment form, end of maintenance form, follow-up form, and survival form. Note that typical RECIST 1.1 indications of progression such as an increase in sum of longest diameters of 20% or the presence of a new lesion are not considered progression for the purposes of PFS.

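### SAP 9.2 dates progression only when treatment ended for deterioration, Appendix 1 takes it from four forms, and no text says which governs a progression first recorded in follow-up

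*SAP*

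**What the plan says.** **SAP 9.2, event definition.** PFS runs from first dose "to either observation of clinical deterioration, removal from study, or occurrence of death due to any cause within 126 days" of the last tumor assessment.

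**SAP 9.2, date rule.** "Progression date will be defined as the end of treatment date as captured per eCRF guidelines", on condition that treatment ended for radiographic or clinical deterioration.

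**SAP 9.2, censoring.** For anyone who lacks a progression date, or who dies beyond the 126-day window, the rule is: "the PFS time will be censored on the date of last tumor assessment or last treatment date". The second of these dates applies when there is no post-baseline assessment. The paragraph then ends: "PFS analyses will consider tumor assessments after treatment discontinuation".

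**SAP Appendix 1, item 5.** Progression is radiographic or clinical deterioration, or death, captured on forms of several kinds. "This includes the end of treatment form, end of maintenance form, follow-up form, and survival form". It states no event date and puts no time limit on death.

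**SAP 9.** "Progressive disease will be determined by clinical or radiological deterioration leading to the subject being taken off-treatment at the discretion of the investigator". Any adequate assessment that is not a complete response, partial response or progression is stable disease.

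**SAP 9.1.** DOR ends at progressive disease or death from any cause, and a Kaplan-Meier median is planned by treatment and subgroup.

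**The concern.** The two definitions cover different sets of subjects. The 9.2 date rule recognizes progression only as a reason for stopping treatment. Appendix 1 also recognizes progression recorded after treatment has stopped. Section 9.2 is not consistent within itself either. Its event definition does not tie clinical deterioration or removal from study to the end of treatment, and it says post-treatment assessments count, yet its date rule gives a progression seen at such an assessment no date.

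Subjects in this position are expected by design. Protocol 5.3 and 12.1.4 and SAP 4.1.4 send subjects who finish treatment without progressing into long-term follow-up, and all three foresee progression there. Protocol Table 13 has follow-up imaging and a visit column for subjects who leave follow-up with progressive disease.

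At stake is whether a progression seen in follow-up enters the analysis as an event, as a censored record or as a later death. As the SAP stands, the programmer's choice of text decides.

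**Working it through.** **Step 1: the one figure in the rule.** SAP 9.2 describes the 126-day death window as about two assessment intervals. SAP 4.4 gives scans every 9 weeks: 2 × 9 × 7 = 126 days. It reproduces.

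**Step 2: when dosing ends relative to the first scan.** Protocol 12.1.3.1 ends five-dose treatment in the E cohorts on day 56. SAP 4.4 puts the first scan at 12 weeks ± 10 days: 84 − 10 = 74 to 84 + 10 = 94. On that schedule, an E-cohort subject without maintenance who completes dosing has the first scheduled response scan 18 to 38 days after the last dose. Barring retreatment (three subjects, SAP 6.7), progression found at that scan cannot be why dosing ended.

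**Step 3: both rules on one hypothetical subject.** The subject completes five doses, and treatment ends for a reason other than deterioration. Scans fall on days 84, 84 + 63 = 147 and 147 + 63 = 210. Radiographic progression is recorded on the follow-up form at day 210, the last assessment.

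| Outcome | Days from last scan to death | 9.2 date rule | Appendix 1 |
|---|---|---|---|
| Alive | – | Censored, day 210 | Progression event |
| Death on day 300 | 300 − 210 = 90 (≤ 126) | Event, day 300 | Progression event |
| Death on day 400 | 400 − 210 = 190 (> 126) | Censored, day 210 | Progression event |

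The Appendix 1 event falls on day 210 if dated at the scan, but the appendix does not say so. In rows one and three the recorded time is then the same and only the event flag differs. In row two the status is the same and the date moves by 90 days.

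**Step 4: DOR.** If the wording in SAP 9 is read literally, the day-210 finding did not lead to removal from treatment and is not progressive disease. DOR would then run on to death, or be censored at the last non-progression assessment or follow-up call (SAP 9.1). If the follow-up progression counts, DOR ends there.

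**Step 5: scale, by assumption only.** Let *f* be the share of progressions first recorded in follow-up. Assume that all subjects progress, that survival after progression is exponential with a median of 8 months, and that the progression scan is the last assessment. None of these values is in the documents. The chance of surviving past the window is 2^(−126 / (8 × 30.4375)) = 2^(−0.517) = 0.699. The share with a PFS event under the 9.2 date rule is 1 − 0.699*f*, against 100% under Appendix 1:

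- *f* = 25%: about 82–83%
- *f* = 50%: about 65%
- *f* = 75%: about 48%

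This shows how the rule behaves. It is not an estimate for this trial.

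**The case against.** **The appendix is the natural text to code.** SAP 7.1 sends the programmer there, and item 5 is the more specific text and names PFS. This has force but sets no precedence. The appendix describes itself as "additional programming instructions to define important variables that are not available in the main SAP text", and progression is defined in the main text. Item 5 also speaks of forms showing that treatment is ending, which could be read narrowly, but two of the four forms it names belong to follow-up.

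**PFS carries little weight here.** This stands. PFS is exploratory, the SAP synopsis and 9.2 plan a listing, and the Kaplan-Meier tables and figures in 9.2 are for overall survival. Only a general sentence in 9.1 says PFS will be summarized by treatment and subgroup.

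**Stronger readings that the documents do not support:**

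- *A reader might infer that every progression after completed treatment becomes censored.* Death within 126 days of the last assessment remains an event, and the opening definition in 9.2 can be read to include clinical deterioration or removal from study during follow-up.
- *A reader might infer a biased PFS comparison of cohorts with and without maintenance.* No such comparison is specified. SAP 7.1 pools across that line (EC2 with EC3, DEC with DEC2).
- *A reader might take it as known how every escalation subject's end of treatment was recorded.* That depends on eCRF guidelines that are not in the documents. DEC subjects also received pembrolizumab, and the body of Supplement A is not available.
- *A reader might assume that every named form carries a scan date.* Survival follow-up collects little beyond vital status (Protocol 5.4, SAP 4.1.5).

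**Conclusion.** The conflict is real and nothing in the documents resolves it. Coding the 9.2 date rule as written would turn a progression first seen in follow-up into a censored record, or into an event at a later death within 126 days of the last assessment. Under Appendix 1 the same progression is an event, with no date specified. The rule therefore misstates outcomes that both documents foresee; it is more than a missing detail.

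The number of subjects affected is unknown. For PFS the consequence is modest, because the endpoint is exploratory and mainly listed. It reaches further through DOR, which has a planned Kaplan-Meier median, and through the treatment-tied wording of progressive disease in SAP 9. The conclusion assumes only that some subjects end treatment for a reason other than deterioration and progress afterwards. It should be corrected, but it does not touch the safety objective.

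**What to change.** State one rule, in the same words, in SAP 9.2 and Appendix 1 item 5:

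1. Progression is the earliest radiographic or clinical deterioration recorded on any of the four named forms.
2. Its date is the scan or assessment date where one is recorded, and otherwise the date on the form.
3. Say whether removal from study without deterioration is an event or a censoring point, and whether the 126-day limit on deaths applies. Appendix 1 currently has no limit.
4. Align the definition of progressive disease in SAP 9 so that it does not require removal from treatment.
5. Use the same progression date for DOR.

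The cost is SAP wording and the matching derivation code, using forms that the SAP already names. Before adopting item 2, check which forms hold a scan or assessment date; the survival form may not. SAP section 2 requires the plan to be final before database lock, so the change belongs before then.

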5.3. Long Term Follow up

Subjects who completed therapy, including treatment with or without retreatment, treatment with maintenance, or discontinued treatment for any reason other than clinical or radiological progression will enter the Long Term Follow up period. Subjects will be evaluated every 8 weeks for one year (until Amendment 5), and every 9 weeks (Amendment 6). During this Long Term Follow up Period, if a subject progresses or receives an intervening anti-cancer therapy, the subject will then enter the Survival Follow up Period.

Subjects who discontinue treatment due to clinical or radiological progression or Withdraw Consent from study treatment(s) will not enter Long Term Follow up, but will enter survival follow up as outlined below.

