4.4. Study Assessments

Details of scheduled assessments are presented in the study Protocol, with clarifications in Administrative letters 7 and 8. Tumor imaging occurred 12 weeks \pm 10 days after first dose and every 9 weeks \pm 10 days thereafter.

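### The PFS censoring sentence in SAP 9.2 contradicts the PFS event definition in the same paragraph (exploratory endpoint)

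*SAP*

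**What the plan says.** SAP 9.2 measures PFS from first dose "to either observation of clinical deterioration, removal from study, or occurrence of death due to any cause", with death counting only inside a window: "occurrence of death due to any cause within 126 days (approximately 2 time intervals for tumor assessments) of the last tumor assessment".

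The next sentence supplies the date: "Progression date will be defined as the end of treatment date as captured per eCRF guidelines", provided the recorded reason for ending treatment is radiographic or clinical deterioration.

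Censoring follows. It applies "In subjects without a progression date or with a death date more than 126 days after the last tumor assessment", and for those subjects "the PFS time will be censored on the date of last tumor assessment or last treatment date", the latter where there is no post-baseline assessment. The paragraph ends by saying that assessments after treatment discontinuation will be considered.

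Three other places bear on the point:

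- **Appendix 1 item 5 of the SAP** defines progression as radiographic or clinical deterioration captured on any of several forms, including the survival form, or death.
- **Protocol 5.3** says that subjects who stop because of progression "will not enter Long Term Follow up, but will enter survival follow up as outlined below". Protocol Table 13 schedules no tumor imaging in survival follow-up.
- **The role of PFS.** It is exploratory. SAP 9.2 and the SAP synopsis give it a listing, SAP 9.1 says it will be summarized by treatment and subgroup, and Protocol 14.3.3 plans a Kaplan-Meier summary.

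**The concern.** The censoring sentence has two limbs joined by *or*, and neither carries an exception. The second limb does not exclude subjects who already have a progression date. The first limb does not exclude subjects whose early death has just been defined as an event. A programmer who follows the sentence would therefore censor subjects whom the definition calls events.

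The first group need not be rare. Someone who stops for progression has no further scheduled scans, so the last assessment stays at about the time of progression. Living a further four months or so and then dying is enough to meet the second limb. PFS status would then depend on what happens after progression: a progressor still alive is an event, and the same subject becomes censored once a late death is recorded. That makes the censoring informative.

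**Working it through.** **The 126-day window.** SAP 4.4 puts the first imaging at 12 weeks ± 10 "days after first dose and every 9 weeks" ± 10 days after that. Two later intervals give 2 × 9 × 7 = 126 days, so the plan's figure reproduces exactly. The first two intervals together give (12 + 9) × 7 = 147 days, a difference that the word *approximately* covers. The window itself is not in question.

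**Truth table.** Each subject is classified by whether 9.2 gives a progression date and by when death occurs relative to the last tumor assessment. A progression date, or a death within 126 days, makes an event. Removal from study is set aside here and taken up below.

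| Progression date (9.2) | Death | Event by definition | Censored by the sentence as written | Conflict |
|---|---|---|---|---|
| No | None | No | Yes | No |
| No | Within 126 days | Yes | Yes (first limb) | **Yes** |
| No | After 126 days | No | Yes | No |
| Yes | None | Yes | No | No |
| Yes | Within 126 days | Yes | No | No |
| Yes | After 126 days | Yes | Yes (second limb) | **Yes** |

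Two of the six cells conflict. Under 9.2's own progression date, the death limb can never produce an event by itself: without a progression date the first limb censors the subject, and with one the event is already the progression.

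**Would replacing *or* with *and* be enough?** No. A bare *and* censors only the cell with no progression date and a late death. Subjects alive without progression would then be neither events nor censored. The rule that agrees with the definition in all six cells is: no progression date, AND (no death OR death more than 126 days after the last assessment).

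**Size of the second-limb conflict.** The documents give no survival rates, so this rests on assumptions: exponential time from last scan to death with median m months, last scan at progression, and follow-up to death. With 30.4375 days per month (the conversion in SAP 8.3), the share of these progressors who are censored is

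P(death more than 126 days after last scan) = 0.5^(126 / (30.4375 × m))

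- m = 3: 0.5^(126/91.31) = 0.384
- m = 6: 0.5^(126/182.63) = 0.620
- m = 9: 0.5^(126/273.94) = 0.727
- m = 12: 0.5^(126/365.25) = 0.787

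A later scan would lower these shares. A last scan that precedes clinical deterioration would raise them.

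**Removal from study.** The definition lists it as an event. If the recorded reason is not deterioration, however, 9.2 gives no progression date and the first limb censors the subject. This is a third mismatch in the same paragraph.

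**The case against.** The strongest defence is that the intent is clear. The paragraph defines events first and then says who is censored, so the second limb most naturally means only that a late death is not itself an event. A careful statistician would probably query the literal version before programming it. That is fair as a reading of intent, but the intended rule is not written down, and the obvious one-word repair fails.

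The second defence is Appendix 1 item 5. SAP 7.1 sends programmers to that appendix, and the item speaks to PFS directly. If death counts as progression, an early death is not clearly a subject without a progression date. This stands in part: the early-death half is better described as a conflict between 9.2 and the appendix than as a settled misclassification. It does not help the progressor who dies late. Nor does the appendix clearly override 9.2, since it is offered for variables not available in the main text.

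The third defence is limited consequence, and it largely stands. PFS is exploratory, and 9.2 specifies Kaplan-Meier medians and figures for OS only. Against that, SAP 9.1 and Protocol 14.3.3 do call for PFS summaries, SAP 13 declares no change from the protocol, and even a listing would carry wrong event flags and times.

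A reader might also infer that the rule removes progressions in the very longest survivors. It does not: a progressor alive at cutoff has no death date and remains an event.

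**Conclusion.** The sentence is wrong as written and should be corrected, with modest consequences. For a subject with a progression date and a death more than 126 days after the last assessment, nothing else in the documents cures the contradiction. For early deaths without a 9.2 progression date, 9.2 contradicts itself and also disagrees with Appendix 1 item 5, so the passages must be reconciled.

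The 38% to 79% range applies only to progressors followed to death, under the assumed medians, exponential form and scan timing. A reader might take it as the share of all progressors, or as proof that a reported median PFS will be inflated by a known factor. The documents support neither: they give no post-progression survival and no rate of follow-up to death, and 9.2 itself specifies no PFS curve.

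The effect is confined to the PFS listing and the summaries named in SAP 9.1 and Protocol 14.3.3, across the three analysis populations in 9.2. The primary safety endpoint, DCR and OS are untouched.

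**What to change.** Replace the event and censoring sentences in SAP 9.2 with wording such as:

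*The PFS event is the earlier of the progression date, or death within 126 days of the last tumor assessment in subjects with no progression date. A later death does not change a recorded progression. Subjects with no progression date AND either no death or a death more than 126 days after the last tumor assessment are censored at the last tumor assessment, or at the last treatment date if there is no post-baseline assessment.*

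Two decisions go with it:

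1. State whether removal from study without a deterioration reason is an event or is censored. The wording above leaves it out, so a sentence must be added either way.
2. Align Appendix 1 item 5 with 9.2: say whether death counts as progression, and which forms supply the progression date, since the appendix draws on more forms than the end-of-treatment date in 9.2.

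The cost is a few sentences in the SAP and appendix and the matching derivation code. No new data are needed. SAP section 2 requires the plan to be final before database lock, so the change belongs before that point.

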12.1.5. Study Participation

Each subject will have their study participation documented, including the number of cycles completed, the duration of the Follow-up Period, and if discontinuing from the study, the reason for discontinuation. At the end of each cycle, the subject continuation status for each subject will be documented on the CRF.

If for any reason, either study treatment or observations were discontinued, the reason will be recorded. The primary reasons for discontinuation will be documented:

- Adverse event(s)
- Protocol violation
- Disease progression (clinical or radiological)
- Subject withdrew consent
- Subject is lost to follow-up
- Death
- Other

Subjects who discontinue from the study should be followed until resolution and/or stabilization of any adverse event. All subjects who discontinue from the study should complete Follow-up Visits to be monitored for 28 days following the last dose of INT230-6 for the occurrence of study drug-related adverse events or other clinically significant adverse event. Subjects who are unable to complete the follow-up visits should be contacted at least once within 28 days following the last dose INT230-6.

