4.1.5. Survival Follow-up Period

Following completion of the treatment and long term follow-up, as applicable, all subjects will be followed for survival. After that initial assessment of all study subjects, any surviving subjects will have their survival status assessed approximately every 3 months by either a telephone or in-person contact until study completion or termination by the Sponsor. With the exception of noting the first use of subsequent anti-cancer therapies, no other data (e.g., subsequent therapies, performance status etc.) beyond survival will be collected during these calls/visits.

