7.6. Handling of Dropouts or Missing Data

Where individual data points are missing because of insufficient samples, dropouts, or other reasons, the data will be analyzed based on reduced denominators (e.g., using the response evaluable population). For survival analysis, dropouts without confirming events will be treated as censored.

All missing and partial start dates will be queried for a value. If a complete start date cannot be obtained, the following imputation rules apply in order to calculate duration of adverse event, concomitant medication use, or prior cancer history endpoints:

- Missing month and day
 - If the year of the incomplete start date is the same as the year of the date of study drug administration, then the missing month and day of the start date will be imputed to be the month and day of the start of study drug administration.
 - If the year of the incomplete start date is before the year of the date of study drug administration, December 31 will be assigned to the missing fields.
 - If the year of the incomplete start date is after the year of the date of study drug administration, January 1 will be assigned to the missing fields.

- Missing month only
 - If only the month is missing, the day will also be treated as missing, and both month and day will be replaced according to the above procedure.
- Missing day only
 - If the month and year of the incomplete start date are the same as the month and year of the date of study drug administration, the start date of study drug will be assigned to the missing field (i.e., AEs will be assumed treatment-emergent, and medications will be assumed concomitant).
 - If the month and year of the incomplete start date are before the month and year of the date of study drug administration, the last day of the month will be assigned to the missing field.
 - If the month and year of the incomplete start date are after the month and year of the date of study drug administration, the first day of the month will be assigned to the missing field.

If the stop date is complete and the imputed start date, when imputed as instructed above, is after the stop date, the start date will be imputed to equal the stop date.

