9.1. Additional Efficacy Analysis

Additional efficacy parameters include the duration of response (DOR), the injected tumor response (ITR), the bystander tumor response (BTR), progression free survival (PFS), and overall survival (OS). These endpoints will be summarized by treatment (see section 7 for definition of each treatment) and subgroup. Other than 1 listing reporting bystander tumors' diameter that declined over time that declined (noted below), the bystander tumor response rate (BTR) analysis will be conducted separately from the SAP from collected radiographic data.

DOR is defined as the time from first tumor assessment of CR, PR, or SD to the time of progressive disease or death due to any cause. For responders with no death or progression, DOR will be censored on the last non-PD tumor assessment or follow-up call.

The median DOR as obtained from Kaplan-Meier methods will be presented by treatment and subgroup and will include the median, 25th percentile, 75th percentile, and a 2-sided point-wise 95% confidence interval.

ITR will be based on the target tumors at the baseline visit; tumors that become target during the study will also be included in the ITR calculation at the time they are treated. The ITR is defined as the ratio of CR + PR in injected tumors / total number of injected tumors. Thus, bystander or non-target lesions dosed at later dates are not included in calculations for ITR.

The ITR will be calculated based on the maximum likelihood estimator and summarized in tables. The estimate of ITR will be accompanied by 2-sided 95% exact binomial confidence intervals as determined by the Clopper-Pearson method and assessed at each study-specified timepoint where an assessment is performed.

The BTR will follow the same definition as the ITR for bystander tumors. Note that bystander tumors that are injected on study will be included in the ITR calculation.

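### Overall survival is censored at an undefined end-of-study date, so subjects with unknown vital status may be credited with follow-up that nobody observed

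*SAP*

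**What the plan says.** SAP section 9.2 defines the endpoint: "OS will be defined as the time (in months) from first dose of INT230-6 to death". One sentence sets the censoring: "Subjects for whom death is not reported will be censored at the date of end of study".

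No definition of the end-of-study date accompanies it. SAP section 8.1 uses the term at subject level, because it tabulates a reason for end of study among treated subjects. The individual date in the disposition listing, however, is called the date of study discontinuation, a name the OS rule does not use. SAP section 7.6 adds only this: "For survival analysis, dropouts without confirming events will be treated as censored". It supplies no date.

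The other time-to-event endpoints are tied to observation. In SAP section 9.2, for subjects without a qualifying event, "the PFS time will be censored on the date of last tumor assessment", or on the last treatment date if there is no post-baseline assessment. In SAP section 9.1, "DOR will be censored on the last non-PD tumor assessment or follow-up call".

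On follow-up, SAP section 4.1.5 has "survival status assessed approximately every 3 months by either a telephone or in-person contact until study completion or termination by the Sponsor". Protocol section 12.1.4 also allows chart review. Protocol section 12.1.5 lists "Subject is lost to follow-up" and withdrawn consent among the reasons for discontinuation. SAP section 4.1.4 sends both groups to survival follow-up, but Protocol section 12.1.6 exempts subjects who withdraw consent for all study procedures.

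**The concern.** A Kaplan-Meier estimate is sound when each subject leaves the risk set at the point where information about that subject stops. The OS rule moves subjects to a later date whenever no death has been reported. Someone lost to follow-up may have died since, and that death may never reach the database. Counting this person as at risk and alive enlarges the denominator without allowing an event, so the curve sits too high.

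OS is an exploratory objective in every cohort (SAP Table 2), but it carries weight. Longer OS is part of the SAP's research hypothesis (section 3.1). OS is the only endpoint with planned Kaplan-Meier figures, drawn for three populations and several subgroups, with optional hazard ratios between curves (section 9.2). In small groups, such as the ipilimumab sarcoma subjects, a few people with unknown status could move a median.

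**Working it through.** The plan gives no OS event count, median, hazard ratio or loss rate, so there is no figure to reproduce. The check has two parts: a comparison of the rules, and an illustration on assumed inputs.

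**Rules side by side**

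| Endpoint | Censoring date | Tied to an observation? |
|---|---|---|
| PFS (SAP 9.2) | last tumor assessment, else last treatment | yes |
| DOR (SAP 9.1) | last non-PD assessment or follow-up call | yes |
| OS (SAP 9.2) | end of study, undefined | not stated |

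**Assumed inputs (none is in the documents).** OS is exponential with true median 12 months, so λ = ln 2 / 12 = 0.05776 per month. A fraction p of subjects is assigned a loss time L, uniform over months 1 to 9 and unrelated to prognosis. A subject is lost only if still alive at L, and later deaths go unreported. Accrual is uniform over 60 months and closure is at month 69, so everyone has at least 9 months of potential follow-up.

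**Closure reading.** A lost subject never has an event. For t of 9 months or more, the curve estimates

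S*(t) = (1 − p)·exp(−λt) + p·m,

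where m is the mean of exp(−λL) = (exp(−λ) − exp(−9λ)) / (8λ) = (0.9439 − 0.5946) / 0.4621 = 0.756.

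Setting S*(t) = 0.5 gives exp(−λt) = (0.5 − 0.756p) / (1 − p):

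- p = 5%: 0.4865, median 12.5 months
- p = 10%: 0.4716, median 13.0 months
- p = 20%: 0.4360, median 14.4 months
- p = 30%: 0.3904, median 16.3 months

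Survival at 12 months is 0.5(1 − p) + 0.756p, which is 53%, 55% and 58% at p = 10%, 20% and 30%, against a true 50%. Because some assigned subjects die first, the share actually lost is 0.756p, or 7.6%, 15.1% and 22.7%. A simulation of the same set-up gave about 13.0, 14.4 and 16.4 months, which agrees within sampling error.

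**Subject-level reading, exit date g months after last contact.** Let A(t) = exp(−λt)·[(1 − p) + p·P(L > t)] be the share alive and truly observed. Let B(t) be the share lost within the previous g months, that is, p/8 times the integral of exp(−λl) over those loss times. The apparent hazard is λ·A/(A + B), integrated numerically. With g = 0, B is zero and the hazard is exactly λ.

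| Assigned loss | Closure | g = 3 months | g = 1 month | g = 0 |
|---|---|---|---|---|
| 5% | 12.5 | 12.2 | 12.1 | 12.0 |
| 10% | 13.0 | 12.3 | 12.1 | 12.0 |
| 20% | 14.4 | 12.7 | 12.2 | 12.0 |
| 30% | 16.3 | 13.1 | 12.4 | 12.0 |

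**Other assumptions.** Here loss occurs at a constant rate instead of in months 1 to 9, at nominal 10%, 20% and 30%.

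- True median 12 months: 12.7, 13.6 and 15.2 on the closure reading; 12.3, 12.5 and 12.9 with a 3-month gap.
- True median 6 months: 6.3, 6.8 and 7.6 on the closure reading; 6.2, 6.5 and 6.9 with a 3-month gap.

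**Early against late enrollees.** Entry date does not appear in S*(t), so with the same loss pattern the inflation does not depend on when a subject enrolled. A simulation with constant-rate loss and true median 10 months agrees. Enrollees in months 0 to 24 had medians of 10.6 and 11.4 months at 10% and 20% loss. Enrollees in months 24 to 60 had 10.5 and 11.3.

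**The case against.** The best defence is that the phrase means each subject's own end-of-study date. SAP section 8.1 supports that reading, and section 7.6, which treats dropouts as censored, fits it. If the case report form sets that date to the last contact, there is no bias. The form guidelines and table shells are not available, so this cannot be excluded. It stands as a possible reading, but the SAP does not say so, and an undefined term that permits different OS results needs defining.

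Second, unknown vital status may be uncommon. Survival is checked about every 3 months, chart review is allowed, and even lost subjects are nominally sent to survival follow-up. Subjects confirmed alive at closure are correctly censored there. All of that stands. It limits the number affected but does not bring it to zero, because a lost subject may be unreachable and some who withdraw are exempt from follow-up.

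Third, OS is exploratory, the study is open-label and non-randomized, and hazard ratios are optional. That lowers the severity.

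A reader might also infer that cohorts enrolled early are inflated most, which would bias the low-loading against high-loading comparison. The documents do not support this. With equal loss the inflation is the same whenever subjects enrolled, and no loss rates by cohort are given. Bias between curves would need loss, or the handling of exit dates, to differ between groups.

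**Conclusion.** The point holds as a fault in specification with a known direction and an unknown size. Followed as written, the rule biases OS upward or leaves it unbiased. The bias is zero if nobody has unknown status or if the recorded date equals last contact. In the main illustration, with 10% to 30% assigned to loss, a true 12-month median becomes about 13.0 to 16.3 months on the closure reading and 12.3 to 13.1 months with a 3-month gap. Every input behind those figures is an assumption, so they show sensitivity and do not estimate this trial's bias.

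It would be tempting to state that the reported OS is inflated by a material amount, or that the main results are compromised. Neither follows. The applicable reading and the number lost are both unknown, and the primary safety endpoint and the disease control rate do not use this rule. Severity: should be fixed, because OS carries the survival hypothesis and the planned figures.

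**What to change.** Replace the OS censoring sentence in SAP section 9.2 with: *Subjects without a reported death are censored at the last date known alive (latest visit, scan, dose, laboratory sample, adverse event record or survival contact), no later than the data cut-off.* State the cut-off date, and report for each Kaplan-Meier curve how many subjects were lost or withdrew with unknown vital status.

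The cost is one sentence, one derived date from data already collected, and one added count per curve. Reported median OS may come out slightly lower. The change does not correct for loss related to prognosis, which is why the counts should be shown.
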